10.1.4 Pregnancy reporting

Pregnancies

In case a female patient becomes pregnant, or plans to become pregnant, the study drug must be discontinued (or, from the date the pregnancy becomes known) for the entire duration of the pregnancy and lactation period (or, for the entire duration that contraception is discontinued). To ensure patient safety, each pregnancy in a patient on study drug must be reported to Novartis within 24 hours of learning of its occurrence. The pregnancy should be followed up to determine outcome, including spontaneous or voluntary termination, details of the birth, and the presence or absence of any birth defects, congenital abnormalities, or maternal and/or newborn complications.

Pregnancy should be recorded on a Clinical Trial Pregnancy Form and reported by the investigator to the local Novartis Patient Safety. Pregnancy follow-up should be recorded on the same form and should include an assessment of the possible relationship to the Novartis study drug of any pregnancy outcome. Any SAE experienced during pregnancy must be reported on the SAE Report Form.

10.1.5 Reporting of study treatment errors including misuse/abuse/overdose

Medication errors are unintentional errors in the prescribing, dispensing, administration or monitoring of a medicine while under the control of a healthcare professional, patient or consumer (EMA definition) (Table 10-1).

Misuse refers to situations where the medicinal product is intentionally and inappropriately used not in accordance with the protocol.

Abuse corresponds to the persistent or sporadic, intentional excessive use of a medicinal product, which is accompanied by harmful physical or psychological effects.

Study treatment errors and uses outside of what is foreseen in the protocol will be recorded on the appropriate eCRF irrespective of whether or not associated with an AE/SAE and reported to Safety only if associated with an SAE. Misuse or abuse will be collected and reported in the safety database irrespective of it being associated with an AE/SAE within 24 hours of Investigator's awareness.

Overdose is any dose and / or regimen which are over the protocol specified dose/regimen.

Table 10-1 Guidance for capturing the study treatment errors including misuse/abuse

Treatment error type	Document in Dosing CRF (Yes/No)	Document in AE eCRF	Complete SAE form
Unintentional study treatment error	Yes	Only if associated with an AE	Only if associated with an SAE
Misuse/Abuse	Yes	Yes	Yes, even if not associated with a SAE
Overdose	Yes	Yes	Only if associated with an SAE

For more information on AE and SAE definition and reporting requirements, please see the respective sections.

10.1.6 Reporting of Non-serious Adverse Drug Reactions

An **adverse drug reaction** (ADR) is a response to a medicinal product which is noxious and unintended. An ADR implies at least a reasonable possibility of a causal relationship between a medicinal product and an adverse event.

Non-serious ADRs that occurred in patients exposed to the Novartis drug(s) of interest must also be recorded in the local Novartis Patient Safety database for local regulatory reporting.

The Novartis drug(s) of interest evaluated in this study is/are: Sacubitril/Valsartan

The treating physician or other involved HCP must assess the relationship to the Novartis drug, complete the AE Report Form and send the completed, signed form by fax/ email within 10 calendar days to the local Patient Safety department.

The email address, telephone and telefax number of the contact persons in the local Patient Safety department, specific to the site, are listed in the treating physician/HCP folder provided to each site. The original copy of the AE Report Form and the fax confirmation sheet or email must be kept with the CRF documentation at the study site.

10.2 Additional safety monitoring

An external central review committee for this study will also periodically review aggregated SAE data, and make recommendation to sponsor if needed, e.g., protocol amendment on inclusion/exclusion criteria. See Section 8.5 in the protocol for details of the external central review committee.

11 Data collection and database management

11.1 Data collection

Designated investigator staff will enter the data required by the protocol into the eCRF. The eCRFs have been built using fully validated secure web-enabled software that conforms to 21 CFR Part 11 requirements, Investigator site staff will not be given access to the Electronic Data Capture (EDC) system until they have been trained. Automatic validation programs check for data discrepancies in the eCRFs, allow modification and/or verification of the entered data by the investigator staff.

The investigator/designee is responsible for assuring that the data (entered into eCRF) is complete, accurate, and that entry and updates are performed in a timely manner. The Investigator must certify that the data entered are complete and accurate.

After final database lock, the investigator will receive copies of the patient data for archiving at the investigational site.

All data should be recorded, handled, and stored in a way that allows its accurate reporting, interpretation, and verification.

11.2 Database management and quality control

Novartis personnel (or designated contract research organization [CRO]) will review the data entered by investigational staff for completeness and accuracy. Electronic data queries stating the nature of the problem and requesting clarification will be created for discrepancies and missing values and sent to the investigational site via the EDC system. Designated investigator site staff are required to respond promptly to queries and to make any necessary changes to the data.

Concomitant treatments and prior medications entered into the database will be coded using the World Health Organization (WHO) Drug Reference List, which employs the Anatomical Therapeutic Chemical (ATC) classification system. Medical history/current medical conditions and adverse events will be coded using the Medical Dictionary for Regulatory Activities (MedDRA) terminology.

11.3 Site monitoring

Before study initiation, at a site initiation visit or at an investigator's meeting, Novartis personnel and/or Novartis designated CRO representative will review the protocol and data capture requirements (i.e. eSource DDE or eCRFs) with the investigators and their staff. During the study, Novartis employs several methods of ensuring protocol and GCP compliance and the quality/integrity of the sites' data. The field monitor will visit the site to check the completeness of patient records, the accuracy of data capture / data entry, the adherence to the protocol and to GCP, the progress of enrollment, and to ensure that study treatment is being stored, dispensed, and accounted for according to specifications. Key study personnel must be available to assist the field monitor during these visits. Continuous remote monitoring of each site's data may be performed by Novartis personnel and/or Novartis designated CRO. Additionally, a central analytics organization may analyze data & identify risks & trends for site operational parameters, and provide reports to Novartis clinical teams to assist with trial oversight.

The investigator must maintain source documents for each participant in the study, consisting of case and visit notes (hospital or clinic medical records) containing demographic and medical information, laboratory data, electrocardiograms, and the results of any other tests or assessments. All information on CRFs must be traceable to these source documents in the patient's file. The investigator must also keep the original informed consent form signed by the patient (a signed copy is given to the patient).

The investigator must give the monitor access to all relevant source documents to confirm their consistency with the data capture and/or data entry. Novartis monitoring standards require full verification for the presence of informed consent, adherence to the inclusion/exclusion criteria, documentation of SAEs, and of data that will be used for all primary variables. Additional checks of the consistency of the source data with the eCRFs are performed according to the study-specific monitoring plan. No information in source documents about the identity of the patients will be disclosed.

12 Data analysis and statistical methods

Any data analysis carried out independently by the investigator should be submitted to Novartis before publication or presentation.

12.1 Analysis sets

The Enrolled Set comprises all patients who enrolled into this study.

The Full Analysis Set (FAS) comprises all patients to whom study treatment has been assigned and who received at least one dose of study treatment. Patients will be analyzed according to the treatment they have been assigned to. Efficacy variables will be analyzed based on the FAS as the primary population.

The Safety Set (SAF) includes all patients who received at least one dose of study treatment. Patients will be analyzed according to the study treatment received. The safety population will be used for the analyses of safety variables.

The Per Protocol Set (PP) includes all patients in the FAS and have no major protocol deviations. PP population will be used for efficacy analysis.

12.2 Patient demographics and other baseline characteristics

Demographic and other baseline data including laboratory test will be listed and summarized descriptively for all patients in the FAS, SAF and PP in separate. Baseline data is defined as data collected during screening phase.

Categorical data will be presented as frequencies and percentages. For continuous data, mean, standard deviation, median, 25th and 75th percentiles, minimum, and maximum will be presented.

Relevant medical histories and current medical conditions at baseline will be summarized by system organ class and preferred term for all patients as well.

12.3 Treatments

Description on how the exposure data for investigational and other treatment medication will be collected by the assessments have been given in Section 6.3. The treatment duration of this study is 12 months (6 months for each treatment) in total. The overall duration will be summarized by treatment group using mean, standard deviation, median, minimum and maximum. The number and percentage of patients will be summarized by treatment group for categorized duration group.

Concomitant medications and significant non-drug therapies prior to and after the start of the study treatment will be listed and summarized according to the ATC classification system for the safety population.

12.4 Analysis of the primary endpoint

The purpose of primary objectives are to explore the effect of ARNI and ACEI/ARB in HFrEF patients with ICD or CRT-D in terms of VA events and in terms of ICD shocks and ATP using primary estimand described in Section 2.1.

In this study, patients will be observed for 6 months under ACEI/ARB alone. Then, ARNI treatment will be initiated (ACEI/ARB stopped, 36-hr washout period applied for patients using ACEI only) and patients will be observed for another 6 months under ARNI.

Multiple primary endpoints will be evaluated in this study during 2 different treatment periods, that are 6 months of ACEI/ARB treatment and 6 months of ARNI treatment (see detailed definitions in Section 12.4.1.)

Since the endpoints are all paired qualitative variable, McNemar Test will be used respectively to assess the difference in primary endpoint proportion between treatments.

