1.2 Purpose

The purpose of this study is to generate effectiveness data of ARNI, in the Chinese HFrEF patients with implanted ICD or CRT-D.

2 Objectives and endpoints

This study aims to explore the effect of ARNI on VA and ICD or CRT-D shocks and ATP. The objectives and related endpoints are further described in Table 2-1.

Table 2-1 Objectives and related endpoints

Objectives	Endpoints			
Primary Objective	Endpoint for primary objective			
To assess the proportion of patients with VA events over 6 months of ACEI/ARB and 6 months of ARNI treatment	Proportion of patients with VA events over 6 months of ACEI/ARB and 6 months of ARNI treatment (VA events are defined as SVT, NSVT and PVC, ICD shock and ATP, the definitions of SVT, NSVT, PVC, ATP are as below)			

Ok	pjectives	Endpoints			
Se	condary Objectives	Endpoints for secondary objectives			
•	To assess the number of occurrences of VA events and ICD or CRT-D shocks over 6 months of ACEI/ARB and 6 months of ARNI treatment	Numbers of NSVT, SVT, PVC, ICD shock and ATP experienced by patients over 6 months of ACEI/ARB and 6 months of ARNI treatment			
•	To compare the changes in LVEF and NYHA level between ACEI/ARB and ARNI treatments	 LVEF (%) over 6 months of ACEI/ARB and 6 months of ARNI treatment NYHA level over 6 months of ACEI/ARB and 6 months of ARNI treatment 			
•	To compare the changes in the NT-proBNP level between ACEI/ARB and ARNI treatments	NT-proBNP (pg/mL) level over 6 months of ACEI/ARB and 6 months of ARNI treatment			
•	To compare the healthcare resource utilization of HF patients during ACEI/ARB and ARNI treatments	Number of hospitalizations for arrhythmia or HF related hospitalizations over 6 months of ACEI/ARB and 6 months of ARNI treatment			

Abbreviations: ACEI = angiotensin-converting enzyme inhibitor;

; ARB = angiotensin receptor blockers; ARNI = angiotensin receptor neprilysin inhibitor; ATP = anti-tachycardia pacing; CRT-D = cardiac resynchronization therapy-defibrillator; HF = heart failure; ICD = implantable cardioverter defibrillator; LVEF = left ventricular ejection fraction; NSVT = non-sustained ventricular tachycardia; NT-proBNP = N-Terminal prohormone of Brain Natriuretic Peptide; NYHA = New York Heart Association; PVC = premature ventricular contraction; SVT = sustained ventricular tachycardia; VA = ventricular arrhythmias

Note

Sustained ventricular tachycardia is defined as tachycardia with hemodynamic disorder or lasting for >30 seconds

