12.4.1 Definition of primary endpoint

The endpoints of primary objective are as follow:

- 1. To explore the effect of ARNI in VA events, ICD shocks and ATP.
 - 1. Paired proportion of patients by the occurrence of at least one SVT over 6 months of ACEI/ARB and 6 months of ARNI treatment
 - 2. Paired proportion of patients by the occurrence of at least one NSVT over 6 months of ACEI/ARB and 6 months of ARNI treatment
 - 3. Paired proportion of patients by the occurrence of at least one PVC over 6 months of ACEI/ARB and 6 months of ARNI treatment
 - 4. Paired proportion of patients by the occurrence of at least one ICD shocks over 6 months of ACEI/ARB and 6 months of ARNI treatment
 - 5. Paired proportion of patients by the occurrence of at least one ATP over 6 months of ACEI/ARB and 6 months of ARNI treatment

The VA event, ICD shocks and ATP assessment will be captured by ICD or CRT-D implanted into the patients.

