12.4.2 Statistical model, hypothesis, and method of analysis

For all primary endpoints, summaries at baseline, Month 3, 6, 9 and 12 post-indexing date will be reported together. Different hypothesis testing will be done on different types of variables as follow:

Analysis of paired patient proportions

Occurrence events to be considered SVT, NSVT, PVC, ICD shocks and ATP.

For each of the occurrence event, number of patients with at least one event stratified by treatments, will be presented in a 2 x 2 contingency table as follow:

Table 12-1 Matched pairs 2 x 2 contingency table

ARNI (case)	ACEI/ARB (control)		
	At least one event	No event	Total
At least one event	а	b	a + b
No event	С	d	c + d
Total	a + c	b+d	N = a + b + c + d

The following statistical hypothesis under 95% significance level will be tested to address the primary objective:

Null hypothesis: $p_b = p_c$ versus alternative hypothesis: $p_b \neq p_c$, where p_b and p_c is b/N and c/N respectively. The test statistic considered is McNemar Test statistic as follow:

$$\chi^2 = \frac{(b-c)^2}{b+c}$$

which has a chi-squared distribution with degree of freedom of one.

However, an exact test (binomial sign test) will be used if the discordant cells have low values (b + c < 25).

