12.8 Sample size calculation

12.8.1 Primary endpoint

McNemar Test is used in the primary analysis to test for 2 correlated proportions. Approximate formula from Machin et al (1997) is used to calculate the minimum size required.

For the proportion of discordant pairs, the following approximate formula is used:

Proportion Discordant =
$$P_t(1 - P_s) + P_s(1 - P_t)$$

where P_t and P_s are proportion of patients experiencing the event of interest during ACEI/ARB and ARNI treatment period respectively. Over here, both proportions are assumed to be similar to de Diego et al (2018)'s study. According to de Diego et al (2018)'s study, SVT (one of the VA event) has the following incidence 8/120 and 1/120 during ACEI/ARB and ARNI treatment period respectively. Hence, by substitute both into the equation above, proportion discordant calculated is 0.0739 after rounding off.

For the difference, a parameter under effect size is approximated by the following formula:

Effect Size =
$$P_t(1 - P_s) - P_s(1 - P_t)$$

and after substituting P_t and P_s defined above, the effect size calculated is -0.0583.

Thus, by considering the parameters defined above, power of 0.8 and significance level of 0.05, the sample size required is 175. Further consider a dropout rate of 20%, the minimum sample size required is 219.

The above calculation is calculated using PASS 11 software's Test for Two Correlated Proportion (McNemar Test) [Differences] procedure.

For proportion of patients had ICD or CRT-D shocks occurrence over 6 months of ACEI/ARB and 6 months of ARNI treatment, the above sample size will provide 95% - 98% power to detect a proportion difference of 0.075 at two-sided significance level of 0.05. The proportion difference is derived from the published literature (de Diego et al 2018).

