7.1 Overall Statistical Considerations

All statistical analyses are performed using SAS9.4.

All subjects related, efficacy related and safety related data should be collected and included in the statistical analysis. Notes or descriptive text records are only listed. For other data, descriptive statistical analysis would be performed, also statistical inference would be applied if needed.

In the statistical tabulations, screening number of subjects is the universal unique identifier of subjects in the study.

General rules of descriptive statistics: Quantitative variables are described by mean, standard deviation, standard error, median, minimum, maximum, Q1 and Q3. Categorical variables are

described by number and percentage of each category. Two-sided 95% confidence intervals will also be calculated for efficacy endpoints.

In the laboratory test part and the efficacy analysis part, 2 digits will be retained for the upper and lower limits of means and their confidence intervals, 3 digits for standard deviations, and 2 digits for medians, minimums, maximums, Q1 and Q3. In other parts, 1 digit more than the original values can be retained for the upper and lower limits of means and their confidence intervals, 2 digits more for standard deviations, and the original value digits for medians, minimums, maximums, Q1 and Q3. One decimal place will be retained for percentages and the upper and lower limits of their confidence intervals (but for efficacy analysis, 2 decimal places will be retained).

General principles of statistical inference: paired t test and Wilcoxon rank sum test will be used to compare quantitative data. McNemar test, exact test (binomial sign test) and Liddell's exact test will be used to compare categorical variables. All statistical tests will be subjected to twosided tests (unless otherwise specified), and a P-value less than or equal to 0.05 will be considered to indicate a statistically significant difference (unless otherwise specified).

For values such as "< xxx", half of the number following the less-than sign will be used to summarize and calculate statistics. For values such as "> xxx", xxx will be used to summarize and calculate statistics. For values such as "xx-xx", the average of the numbers before and after "-" will be used to summarize and calculate statistics. P value is rounded to 4 decimal places. If P < 0.0001, it is presented as '< .0001'; if P > 0.9999, it is presented as '> .9999'.

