7.4 Efficacy Analysis

7.4.1 Efficacy analysis of primary endpoint

The analysis will be based on the efficacy analysis set and the per protocol set.

- Proportion of paired patients who developed at least one SVT over 6 months of ACEI/ARB and 6 months of ARNI treatment.
- Paired proportion of patients by the occurrence of at least one NSVT over 6 months of ACEI/ARB and 6 months of ARNI treatment.
- Paired proportion of patients by the occurrence of at least one PVC over 6 months of ACEI/ARB and 6 months of ARNI treatment.
- Paired proportion of patients by the occurrence of at least one ICD or CRT-D shock over 6 months of ACEI/ARB and 6 months of ARNI treatment.
- Paired proportion of patients by the occurrence of at least one ATP event over 6 months of ACEI/ARB and 6 months of ARNI treatment.

Different hypothesis testing will be done on different types of variables:

Analysis of paired patient proportion

Occurrence events to be considered are SVT, NSVT, PVC, ICD or CRT-D shocks and ATP.

For each of the occurrence event, number of patients with at least one event stratified by treatments, will be presented in a 2×2 contingency table as follow:

ARNI (case)	ACEI/ARB (control)		
	At least one event	No event	Total
At least one event	a	b	a + b
No event	С	d	c + d
Total	a + c	b + d	N = a + b + c + d

Table 5-1 Matched pairs 2 × 2 contingency table

The following statistical hypothesis under 95% significance level will be tested to address the primary objective:

Null hypothesis: $p_b = p_c$ versus alternative hypothesis: $p_b \neq p_c$, where p_b and p_c are b/N and c/N, respectively. The test statistic considered is McNemar Test statistic as follow:

$$\chi^2 = \frac{\left(b-c\right)^2}{b+c}$$

which has a chi-squared distribution with degree of freedom of one.

However, an exact test (binomial sign test) will be used if the discordant cells have low values (b + c < 25).

Supportive analyses

In addition to the primary analysis, all the paired proportion will also be analyzed using the Liddell's exact test (Liddell 1983) as supportive analysis. From Table 5-1, the maximum likelihood estimate of relative risk (Mantel and Haenszel 1959), \hat{R} is given as follow:

$$\widehat{R} = \frac{b}{c}$$

Null hypothesis: $\hat{R} = 1$ versus alternative hypothesis: $\hat{R} \neq 1$ The test statistic considered, *F* is given as follow:

$$F = \frac{b}{c+1}$$

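### Five primary endpoints are each tested at two-sided 0.05 with no visible rule for meeting the primary objective, and the plan both explores and formally tests them

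*Protocol*

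**What the plan says.** **Number of endpoints.** Protocol 12.4 announces that "Multiple primary endpoints will be evaluated in this study during 2 different treatment periods" and applies McNemar's test to each. Protocol 12.4.1 lists the paired proportions with at least one SVT, NSVT, PVC, shock or ATP. SAP 7.4.1 repeats the list: "Occurrence events to be considered are SVT, NSVT, PVC, ICD or CRT-D shocks and ATP".

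**Formal testing.** Protocol 12.4.2 introduces null and alternative hypotheses with the sentence "The following statistical hypothesis under 95% significance level will be tested to address the primary objective", and SAP 7.4.1 does the same. SAP 7.1 sets the level for every test unless otherwise specified: "a P-value less than or equal to 0.05 will be considered to indicate a statistically significant difference". SAP 7.4.1 sets no other level.

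**Exploratory wording.** Protocol Section 2 says "This study aims to explore the effect of ARNI on VA and ICD or CRT-D shocks and ATP". Protocol 12.4 says "The purpose of primary objectives are to explore the effect of ARNI and ACEI/ARB in HFrEF patients with ICD or CRT-D", and 12.4.1 heads its list "To explore the effect of ARNI in VA events, ICD shocks and ATP".

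**Sample size.** Protocol 12.8.1 rests on one endpoint: "SVT (one of the VA event) has the following incidence 8/120 and 1/120 during ACEI/ARB and ARNI treatment period respectively". From this it derives 175 patients at power 0.8 and alpha 0.05, and 219 after 20% dropout. It also quotes power for shocks at the same unadjusted 0.05. It does not call SVT the lead endpoint.

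**Not in the visible text.** There is no statement that one, all or a particular one of the five tests decides the primary objective. A global testing strategy is mentioned for the secondary variables (Protocol 12.8.2, SAP 3.2.2) but not described.

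**The concern.** The primary objective has five tests and no rule that turns five p-values into one answer. Suppose SVT gives p = 0.20 and shocks give p = 0.03. If any one test is enough, the objective is met. If all five must succeed, or if SVT leads, it is not met. If the tests are exploratory, there is no verdict to give. The same data support all three statements.

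Each reading also has different error properties. Any-of-five does not generally hold 0.05 for the objective. All-of-five does, but its power cannot exceed that of SVT, the endpoint the trial was sized on. Under the exploratory reading neither property matters, but then the text should not say that the hypotheses are tested to address the primary objective.

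The study is open-label, and Protocol 4.5 has all endpoints analysed at an interim. A rule settled late could therefore be seen as chosen with knowledge of the results.

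**Working it through.** **1. Reproduce the sample size.** Inputs from Protocol 12.8.1: 8/120 under ACEI/ARB and 1/120 under ARNI.

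- Event under ACEI/ARB only: (8/120)(119/120) = 0.0661. Event under ARNI only: (1/120)(112/120) = 0.0078.
- Discordance: 0.0661 + 0.0078 = 0.0739. Difference: 0.0661 − 0.0078 = 0.0583. Both match the plan in absolute value.
- Power under the plan's own rule (exact sign test if b + c < 25, otherwise McNemar chi-square), with the number of discordant pairs Binomial(N, 0.0739): 0.799 at 174 pairs, **0.802 at 175**, 0.900 at 219.
- 175/0.8 = 218.75, rounded up to 219.

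So 175 is the smallest number of pairs that gives 80% power with the whole 0.05 spent on SVT. It contains no allowance for the other four tests.

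**2. Textbook figure.** Five independent tests of exact size 0.05: 1 − 0.95^5 = 0.226.

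**3. Size under the plan's own test rule.** With few discordant pairs the sign test is conservative. About 175 × 0.0739 = 12.9 discordant pairs are expected for SVT, and the true null size is 0.0254.

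To illustrate any-of-five, assume the same event rate p in both periods and within-patient correlation r between periods, so that discordance = 2p(1 − p)(1 − r). The SVT rate of 3.84% is chosen to return 0.0739 at r = 0. The other rates and all values of r are assumptions, because the documents give none. Exact null size at 175 pairs:

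| Endpoint (assumed rate) | r = 0 | r = 0.5 | r = 0.7 |
|---|---|---|---|
| SVT (3.84%) | 0.0254 | 0.0141 | 0.0046 |
| Shock (5%) | 0.0289 | 0.0190 | 0.0087 |
| ATP (10%) | 0.0491 | 0.0281 | 0.0211 |
| NSVT (30%) | 0.0507 | 0.0494 | 0.0355 |
| PVC (99%) | 0.0033 | 0.0002 | 0.0000 |
| **Any of these five, independent** | **0.148** | **0.107** | **0.069** |
| **Any of five, all as sparse as SVT, independent** | **0.120** | **0.068** | **0.023** |

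The last two rows are 1 minus the product of (1 − size); for example 1 − 0.9746 × 0.9711 × 0.9509 × 0.9493 × 0.9967 = 0.148.

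**4. Price of an equal alpha split.** SVT power at 175 pairs is 0.722 at alpha 0.025 (two ways) and 0.554 at alpha 0.01 (five ways).

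**The case against.** The best defence is that this is a Phase IV, single-arm, open-label study whose text says three times that it explores. Hypothesis tests in an exploratory study are not a contradiction in themselves, and the plan never promises one overall verdict. Each endpoint's table and p-value can be read as they stand. This argument lowers the severity. It does not remove the point, because Protocol 12.4.2 and SAP 7.4.1 tie the tests to the primary objective and 12.8.1 powers the trial for one of them.

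A second defence is that a rule may sit in text that is not visible. Protocol 12.6 and whatever follows SAP 7.4.2 cannot be seen, and a global testing strategy is named. This limits confidence. However, Protocol 12.4 to 12.4.7 and SAP 7.4.1, where a rule for the primary endpoints would belong, are visible and contain none.

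Two further charges that a reader might bring are not supported:

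- **The 3-month repeat adds unlabelled primary tests.** It stands under the supportive-analyses heading of SAP 7.4.1, so on its face it is already supportive.
- **The interim inflates the error by a calculable amount.** Protocol 4.5 gives its purpose as futility, safety and sample-size re-evaluation, with no efficacy claim. SAP 3.4 counts 117 subjects, including early withdrawals after one ARNI dose, whereas Protocol 12.4.4 analyses complete pairs. The documents do not give the number of interim pairs, so no interim error figure can be computed.

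**Conclusion.** The point stands. Five primary tests at two-sided 0.05 have no visible rule that decides the primary objective, and their status is described in two ways. Individual results can be read; primary success or failure cannot.

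If any one significant test counted, the error rate would not be controlled at 0.05. In the illustrations it runs from about 15% down to 7% for the assumed mix, and from 12% down to 2% for five endpoints as sparse as SVT, as within-patient correlation rises from 0 to 0.7. All of these assume 175 complete pairs, independent endpoints, and event rates and correlations that the documents do not supply.

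A reader might infer that the plan carries a 22.6% false-positive risk, or that inflation is certain unless the five events nearly coincide. Neither follows. The 22.6% is only the textbook value for five independent full-size tests. It is neither an estimate for this trial nor a strict ceiling, since five independent tests of size 0.0507 give 1 − 0.9493^5 = 0.229. Rare events or strong within-patient correlation can bring the error below 5%. The undescribed global testing strategy is a matter to clarify, not proof of a gap.

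This should be fixed. Confidence is moderate, because of the exploratory wording and the text that is not visible.

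**What to change.** Choose one of the following and write it into Protocol 12.4 and SAP 7.4.1.

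- **(a) Confirmatory.** Name SVT, the existing basis of N, as the single primary endpoint at two-sided 0.05, with the other four secondary; or put SVT first in a fixed sequence stated in advance. State that the 6-month final analysis in one named efficacy set decides. This means reconciling Protocol 12.1, which names the full analysis set, with SAP 6, which names an efficacy set requiring at least one ARNI dose. State also that the interim makes no efficacy claim. Justify the choice of SVT by Protocol 12.8.1, not by data already seen. N = 219 and 80% SVT power at 175 pairs are unchanged. The cost is that the other four endpoints lose stand-alone primary status and the estimand in Protocol 2.1, which covers VA, shocks and ATP, has to be narrowed to match. An equal five-way split of alpha would instead reduce SVT power to 55%.
- **(b) Exploratory.** Label all five tests exploratory and remove the confirmatory wording from Protocol 12.4.2 and SAP 7.4.1. Only wording changes; the cost is giving up a confirmatory claim.

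Under either option, describe or delete the global testing strategy in Protocol 12.8.2 and SAP 3.2.2. The 3-month analysis needs no change. Both options need a written protocol amendment (Protocol 14.1) and an SAP update.
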